6.7.3.2. Dose Modifications and Toxicity Management for JTX-2011 in Combination with Nivolumab

For dose modifications for nivolumab please follow the prescribing information (Opdivo® Full Prescribing Information {Bristol-Myers Squibb Company 2017a}). In the event of a toxicity that requires that study treatment be withheld until resolution to Grade 0 or 1, the first administration of study drug after resolution of toxicity should be JTX-2011 alone. Nivolumab may be added at the next dose, at the discretion of the investigator and the medical monitor, if the toxicity does not recur with JTX-2011 monotherapy.

6.7.3.3. Dose Modifications and Toxicity Management for JTX-2011 in Combination with Ipilimumab

For dose modifications for ipilimumab please follow the prescribing information (Yervoy® Full Prescribing Information {Bristol-Myers Squibb Company 2017b}). In the event of a toxicity that requires that study treatment be withheld until resolution to Grade 0 or 1, the first administration of study drug after resolution of toxicity should be JTX-2011 alone. Ipilimumab may be added at the next dose, at the investigator's discretion, if the toxicity does not recur with JTX-2011 monotherapy.

6.7.3.4. Dose Modifications and Toxicity Management for JTX-2011 in Combination with Pembrolizumab

For dose modifications for pembrolizumab please follow the prescribing information (Keytruda® Full Prescribing Information {Merck & Co Inc 2017}). In the event of a toxicity that requires that study treatment be withheld until resolution to Grade 0 or 1, the first administration of study drug after resolution of toxicity should be JTX-2011 alone. Pembrolizumab may be added at the next dose, at the investigator's discretion, if the toxicity does not recur with JTX-2011 monotherapy.

6.7.4. Infusion-Related Reactions

Subjects must be observed for at least 1 hour after completion of infusion of JTX-2011, nivolumab, ipilimumab, and pembrolizumab. In the event of acute hypersensitivity or other infusion reaction, institutional protocol should be initiated and a blood sample drawn for cytokines (NOTE: To be collected at the site and sent out to a Central Laboratory for analysis. Please reference Lab Manual for more details). Signs and symptoms of an infusion reaction may include the following: headache, fever, facial flushing, pruritus, myalgia, nausea, chest tightness, dyspnea, vomiting, erythema, abdominal discomfort, diaphoresis, shivers, hypertension, hypotension, lightheadedness, palpitations, urticaria and somnolence. Although unlikely, serious allergic reactions (e.g., anaphylaxis) may occur at any time during the infusion.

6.7.4.1. Grade 2 Infusion-Related Reactions

In the case of Grade 2 occurrence of signs and symptoms consistent with infusion related reaction, follow institutional protocol and reduce the rate of infusion of JTX-2011 to half the initial rate; consider interrupting infusion of JTX-2011 if symptoms do not respond to medical intervention. If signs and symptoms resolve with intervention including interruption of JTX-2011, JTX-2011 infusion may be restarted at half the initial rate.

6.7.4.2. Grade 3 Infusion-Related Reactions

In the case of Grade 3 or greater occurrence of signs and symptoms consistent with infusion related reaction, discontinue infusion of JTX-2011.

6.7.4.3. Infusion- Related Reaction Prophylaxis

No prophylaxis for infusion related reactions should be administered prior to the Cycle 1 Day 1 dose of study drug. For subjects that experience a Grade 2 or 3 infusion-related reaction and remain on treatment, institutional practice for prevention of infusion reactions should be followed for all subsequent cycles.

Once the Phase 2 cohorts for any part of the trial have been initiated, the Sponsor may administratively allow for infusion reaction prophylaxis (as per institutional guidelines) beginning prior to study drug dosing on CID1.

6.8. Withdrawal of Subjects

A subject is free to withdraw from treatment or from follow-up at any time for any reason without prejudice to their future medical care by the physician or at the institution. However, subjects who withdraw from treatment should be encouraged to return for the end-of-treatment visit, complete all safety assessments, and enter long-term follow-up. If a subject refuses to undergo the end-of-treatment procedures, the reason for refusal should be fully documented in the patient's electronic Case Report Form (eCRF). Subjects who withdraw from follow-up should not be followed for any of the visits and assessments described above.

The Investigator or Jounce may also withdraw the subject from treatment at any time in the interest of his or her safety. The primary reason for withdrawal must be recorded in the subject's medical record and on the withdrawal form in the eCRF. If a subject is withdrawn for more than one reason, each reason should be documented in the source document and the most medically significant reason should be entered on the eCRF.

The withdrawal of a subject from treatment should be discussed where possible with the Medical Monitor before the subject stops taking study drug. If study treatment is discontinued, the final evaluations will be performed as completely as possible.

The reason for termination, date of stopping study treatment and the total treatment period must be recorded in the eCRF and source documents.

6.8.1. Criteria for Withdrawal

The Medical Monitor may be contacted on a case-by-case basis if clarification is required. Reasons for withdrawal include:

- Withdrawal of consent by the subject or refusal by the subject to continue treatment and/or procedures/observations;
- Radiographic or clinical disease progression with or without a requirement for alternative treatment for the condition under study;
- Occurrence of unmanageable adverse events in the judgment of the Investigator or subject, justifies withdrawal due to its severity, nature, or requirement for treatment, regardless of the causal relationship to study drug;

- Pregnancy;
- If the Investigator feels it is in the subject's best interest to withdraw;
- Other reasons (e.g., significant protocol violation, non-compliance, lost to follow-up);
- Termination of the study by Sponsor.

6.8.2. Subject Replacement

Subjects enrolled in Parts A, B, E or G dose escalation cohorts who withdraw from treatment or are lost-to-follow-up prior to completion of Cycle 2 Day 1 assessments will need to be replaced, unless the subject has experienced a DLT.

6.9. Pre-Screening for ICOS Expression

Subjects who have archival biopsy samples available for submission to the central lab for measurement of ICOS expression may provide informed consent for submission of archival samples for evaluation prior to undergoing the informed consent process and screening for full study participation. A separate abbreviated Informed Consent Form will be provided to sites to utilize for this purpose upon approval by their governing IRB. In situations where a subject's archival samples are completely exhausted, subjects may elect to have a biopsy performed per institutional guidelines to serve as an archival sample. Results from ICOS testing of archival tissue performed prior to the 28-day screening window will not need to be repeated.

7. OVERALL STUDY ASSESSMENTS AND FOLLOW-UP

The total study duration is anticipated to be 24-30 months. Each subject's participation on treatment will last a minimum of approximately 3-4 months, including:

- Up to a 28-day screening period;
- 1 cycle (3 or 6 weeks) of study treatment. However, subjects may continue to receive additional cycles of study treatment as long as, in the judgement of the Investigator, the subject may be deriving clinical benefit;
- End of Treatment visit performed 28 days (\pm 7 days) after the last dose of study treatment;

7.1. Screening (All Parts)

Subject eligibility for the study will be determined \leq 28 days prior to initiating study treatment.

The following clinical assessments will be performed during screening:

- Signing of informed consent form.
- Review of eligibility criteria. Eligibility should be confirmed prior to the first dose of study drug(s).
- Subject medical history, disease history, demographics, physical examination including vital signs, height, and weight.
- ECOG performance status assessment.
- Laboratory Assessments: Chemistry, hematology, coagulation, thyroid function and urinalysis.
- Blood samples for Immunophenotyping and Target Engagement.
- 12-lead ECG.
- Ensure archival tumor tissue is available if not already required for pre-screening.
- Radiologic assessment (within 28 days prior to C1D1). CT scan is preferred; however, whichever modality is used at screening should be repeated throughout the trial.
- Optional Brain MRI to confirm stable brain metastasis.
- Record concomitant medications.
- Serum or urine pregnancy test for women of child-bearing potential (WOCBP). The pregnancy test will not be required for women who are surgically sterile or who are greater than 1 year post-menopausal.
- AP1, AP2, BP1, BP2, Parts C, D, F, G, and H only:
 - Fresh tumor tissue biopsy prior to dosing on C1D1.
- Prostate cancer subjects in Parts E and F only:
 - Bone Scan.

7.2. Treatment Period

7.2.1. Cycle 1 Day 1 (All Parts)

The following evaluations and procedures will be performed during this visit:

Any assessments or labs that were performed or obtained within 72 hours of Cycle 1 Day 1 do not need to be repeated.

- Physical examination;
- Vital signs pre-and post-infusion;
- Weight;
- ECOG performance status;
- Pregnancy test for WOCBP;
- 12-lead ECG;
- Laboratory assessments including chemistry, hematology, coagulation, thyroid function, and urinalysis;
- Blood samples for PK/ADA/NAb, Cytokines, Immunophenotyping, Target Engagement, RNA and DNA;
- Record concomitant medications;
- Adverse events assessment;
- JTX-2011 administration followed by observation for at least 1 hour;
- Parts B and D only:
 - Nivolumab administration followed by observation for at least 1 hour;
- Parts E and F only:
 - Ipilimumab administration followed by observation for at least 1 hour;
 - PSA
- Parts G and H only:
 - Pembrolizumab administration followed by observation for at least 1 hour.

7.2.2. Cycle 1 Day 2 (All Parts)

The following evaluations and procedures will be performed during this visit:

- Vital signs;
- Blood sample for PK, Cytokines, Immunophenotyping, Target Engagement;
- Record concomitant medications;
- Adverse events assessment.

7.2.3. Cycle 1 Day 4 (Part A, B, E, and G Sentinel Subjects Only)

- Targeted Physical Exam (as per institutional guidelines);
- Vital signs;
- Record concomitant medications;
- Adverse events assessment.

7.2.4. Cycle 1 Day 8 (Parts A, B, E, and G only, including AP1, AP2, BP1, BP2)

The following evaluations and procedures will be performed during this visit:

- Vital signs;
- Targeted Physical Exam (as per institutional guidelines)

- Laboratory Assessments: Chemistry, Hematology, Coagulation;
- Blood samples for PK, Immunophenotyping, and Target Engagement;
- Record concomitant medications;
- Adverse events assessment.

7.2.5. Cycle 1 Day 15 (Parts A and B [inc. AP1, AP2, BP1, BP2], E, and G only)

The following evaluations and procedures will be performed during this visit:

- Vital signs;
- Laboratory Assessments: Chemistry, Hematology, Coagulation;
- Blood samples for PK and Target Engagement;
- Record concomitant medications;
- Adverse events assessment.

7.2.6. Cycle 1 Day 22 (All cohorts in Parts E and F, q6w cohorts only in Parts C and H)

The following evaluations and procedures will be performed during this visit:

- Targeted Physical Exam.
- Laboratory Assessments: Chemistry, Hematology, Coagulation.
- Blood samples for PK/ADA/NAb, Cytokines, Immunophenotyping, Target Engagement.
- Record concomitant medications.
- Adverse events assessment.
- Part C (q6w) only:
 - Vital signs.
- Parts E and F only:
 - Weight.
 - Vital signs pre-and post-infusion.
 - Ipilimumab administration followed by observation for at least 1 hour.
- Part H only:
 - Weight.
 - Vital signs pre-and post-infusion.
 - Pembrolizumab administration followed by observation for at least 1 hour.

7.2.7. Cycle 2 Day 1 (All Parts)

The following evaluations and procedures will be performed during this visit (\pm 3 days):

- Targeted physical examination.
- Vital signs pre-and post-infusion.
- Weight.
- ECOG performance status.
- Pregnancy test for WOCBP.
- 12-lead ECG.

- Laboratory assessments: Chemistry, hematology, coagulation, thyroid function, and urinalysis. Laboratory assessments need not be repeated if they were performed within 72 hours of Cycle 2 Day 1.
- Blood samples for PK/ADA/NAb, Cytokines, Immunophenotyping, Target Engagement, and RNA.
- Record concomitant medications.
- Adverse events assessment.
- JTX-2011 Administration followed by observation for at least 1 hour.
- AP1, AP2, BP1, BP2, Parts C and F only:
 - Post-treatment fresh tumor biopsy
 - For q3w subjects: (Any timepoint after the C2D1 JTX-2011 dose and prior to the C3D1 JTX-2011 dose.
 - For q6w subjects: Any timepoint after the C2D1 JTX-2011 dose and prior to C2D22
- Parts B and D only:
 - Nivolumab administration followed by observation for at least 1 hour.
- Parts E and F only:
 - Ipilimumab administration followed by observation for at least 1 hour.
- Prostate cancer subjects in Parts E and F only:
 - Bone Scan.
- Parts G and H only:
 - Pembrolizumab administration followed by observation for at least 1 hour.

7.2.8. Cycle 2 Day 22 (All cohorts in Parts E and F, q6w cohorts only in Parts C and H)

The following evaluations and procedures will be performed during this visit (\pm 3 day):

- Physical examination;
- Laboratory Assessments: Chemistry, Hematology, Coagulation;
- Blood samples for PK/ADA/NAb, Target Engagement, and Immunophenotyping;
- Record concomitant medications.
- Adverse events assessment.
- Part C only:
 - Vital signs.
- Parts E and F only:
 - Weight.
 - Vital signs pre-and post-infusion.
 - Ipilimumab administration followed by observation for at least 1 hour.
- Part H only:
 - Weight.
 - Vital signs pre-and post-infusion.
 - Pembrolizumab administration followed by observation for at least 1 hour.

7.2.9. Cycle 3 Day 1 and Day 1 of Subsequent Cycles (All Parts)

The following evaluations and procedures will be performed during this visit (\pm 3 days):

- Physical examination.
- Vital signs pre-and post-infusion.
- Weight.
- ECOG performance status.
- Pregnancy test for WOCBP.
- 12-lead ECG.
- Laboratory assessments: Chemistry, hematology, coagulation, thyroid function, and urinalysis. Laboratory assessments need not be repeated if they were performed within 72 hours of Cycle 3 Day 1 or subsequent Day 1s.
- Blood samples for PK/ADA/NAb, Cytokines, Target Engagement, and Immunophenotyping.
- Blood sample for RNA (at Cycle 4 for q6w cohorts or Cycle 7 for q3w cohorts).
- Record concomitant medications.
- Adverse events assessment.
- JTX-2011 administration followed by observation for at least 1 hour.
- Parts B and D only:
 - Nivolumab Administration followed by observation for at least 1 hour.
- Parts E and F only:
 - Ipilimumab Administration followed by observation for at least 1 hour.
- Prostate cancer subjects in Parts E and F only:
 - PSA.
- Parts G and H only:
 - Pembrolizumab administration followed by observation for at least 1 hour.

7.2.10. Cycle 3 Day 22 and Day 22 of Subsequent Cycles (All cohorts in Parts E and F, q6w cohorts only in Parts C and H)

The following evaluations and procedures will be performed during this visit (\pm 3 day):

- ECOG performance status.
- 12-lead ECG.
- Laboratory Assessments: Chemistry, Hematology, Coagulation.
- Blood samples for PK/ADA/NAb, Target Engagement, and Immunophenotyping.
- Record concomitant medications.
- Adverse events assessment.
- Parts C, E, and F only:
 - Vital signs
- Part H only:
 - Weight.
 - Vital signs pre-and post-infusion.

- Pembrolizumab administration followed by observation for at least 1 hour.

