
Overview of Study Design:
	
This is a Phase 1/2, open label, multicenter, first-in-human trial to evaluate the safety and tolerability, PK, pharmacodynamics, and preliminary efficacy of the ICOS agonist monoclonal antibody JTX-2011 as monotherapy, in combination with nivolumab, in combination with ipilimumab, and in combination with pembrolizumab in adult subjects with advanced and/or refractory solid tumor malignancies. The study is divided into 8 parts. Subjects may be enrolled into any open cohorts for which they qualify at the discretion of the Investigator.
 
Phase 1 Parts
 
Part A (JTX-2011 Monotherapy Dose Escalation) – Completed Enrollment Part A comprises escalating doses of JTX-2011 administered intravenously (IV) q3w in consecutive cohorts, plus Safety/PK/PD Expansion cohorts (AP1 and AP2) at each of two or more dose levels.
 
Part B (JTX-2011 + Nivolumab Combination Dose Escalation) – Completed Enrollment Part B comprises escalating doses of JTX-2011 in combination with nivolumab (both agents administered IV q3w in consecutive cohorts, plus Safety/PK/PD Expansion Cohorts [BP1 and BP2] at each of two or more dose levels).
 
Part E (JTX-2011 + Ipilimumab Combination Dose Escalation) Part E comprises escalating doses of JTX-2011 in combination with ipilimumab in consecutive cohorts (JTX-2011 will be administered IV q6w; ipilimumab will be administered IV q3w for a maximum of 4 doses).
 
Part G (JTX-2011 + Pembrolizumab Combination Dose Escalation) Part G comprises JTX-2011 in combination with pembrolizumab (JTX-2011 and pembrolizumab will be administered IV q3w). Subjects in Part G are required to have a fresh tumor biopsy during screening. In situations where archival tissue is not available or biopsies are not feasible (e.g., would expose the subject to unreasonable health risks), one or more of these requirements may be waived after discussion with the Medical Monitor.
 
Phase 2 Parts
 
Part C (JTX-2011 Monotherapy Phase 2) Part C will include eight (8) cohorts in the indications listed below. Each cohort will enroll approximately 15 subjects per cohort. The JTX-2011 dose in Part C is 0.3 mg/kg at both the q3w and q6w dosing schedule. All subjects must have progressed on or after all approved therapies. If prior therapy included a PD-1 inhibitor, subjects must have progressed after at least 2 months of this therapy.
 
q3w JTX-2011
 
 ○ C01: HNSCC; ○ C02: NSCLC;

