3.4. Ipilimumab Dosage and Administration

Ipilimumab, marketed as Yervoy[®], is a human IgG1 κ cytotoxic T-lymphocyte antigen 4 (CTLA-4)-blocking antibody manufactured by Bristol-Myers Squibb for the treatment of melanoma. Ipilimumab binds to CTLA-4 and blocks the interaction of CTLA-4 with its ligands, CD80/CD86. Ipilimumab, in this study, will be administered as a 90-minute IV infusion (-5/+10 minutes), 3 mg/kg q3w for a total of four doses. Please refer to the Pharmacy Manual and the Yervoy[®] Full Prescribing Information {Bristol-Myers Squibb Company 2017b} for more information.

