5.3. Part E (JTX-2011 in Combination with Ipilimumab Dose Escalation)

Part E comprises escalating doses of JTX-2011 in combination with ipilimumab in consecutive cohorts (JTX-2011 will be administered IV q6w and will be administered until a subject meets criteria for discontinuation; ipilimumab will be administered IV q3w for up to 4 doses).

Three (3) dose escalation cohorts are planned at doses of 0.03 mg/kg, 0.1 mg/kg, and 0.3 mg/kg (approximately 3 dose levels with a minimum of 3 or up to 6 subjects per dose level, exclusive of replacement subjects and evaluation of escalation dose levels [approximately 18 subjects]). A dose de-escalation cohort of 0.01 mg/kg of JTX-2011 may be explored.

Table 3: Part E Dose Escalation Schema

Cohort	JTX-2011 Dose
E63	0.3 mg/kg
E62	0.1 mg/kg
E61*	0.03 mg/kg
E60	0.01 mg/kg

* Starting dose level

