¹² For subjects discontinuing treatment for reasons other than disease progression, radiologic assessment will be conducted every 12 weeks (\pm 2 weeks) during the long-term follow-up period until confirmed disease progression or another anti-cancer therapy is initiated.

¹³ Adverse events will be followed up to 28 days post last dose. As the EOT visit can occur anywhere between 21-35 days post last dose any ongoing AEs at the time of the EOT visit can be followed via other contact (e.g., phone or email) up to 28 days post dose. If an SAE occurs 28 days after last dose administered, the event will only be followed if assessed to be at least possibly related to study drug.

¹⁴ Optional Brain MRI to determine eligibility of subjects with documented history of brain metastasis.

¹⁵ Survival can be followed via phone call or email, a clinic visit is not required.

¹⁶ For subjects with prostate cancer only.

¹⁷ If ipilimumab doses are missed on C1D22, C2D1, or C2D22, they can be made up q3w beginning on C3D1. Each subject may receive up to four total doses of ipilimumab.

¹⁸ Ipilimumab PK, ADA, and NAb are only to be collected on C3D1 and beyond if ipilimumab is administered at those visits.

Table 14: Phase 1 q3w in Part G (JTX-2011 + Pembrolizumab)

Timing of Visit	Screening	Cycle 1				Cycle 2	Cycle 3	Cycle 4	Cycle 5	Cycle 6	Cycle 7	Cycle 8 and Beyond	End of Treatment	Long-Term Follow-up
		Day 1	Day 2	Day 4 ¹⁴	Day 8									
Informed Consent	X													
Eligibility Criteria	X	X												
Medical History	X													
Demography	X													
Physical Exam ¹	X	X		X	X ⁴	X ⁴	X ⁴	X ⁴	X ⁴	X ⁴	X ⁴	X		
Weight (kg)	X	X			X ⁴	X ⁴	X ⁴	X ⁴	X ⁴	X ⁴	X ⁴			
ECOG PS	X	X			X ⁴	X ⁴	X ⁴	X ⁴	X ⁴	X ⁴	X ⁴	X		
ECG	X	X ⁴			X ⁴	X ⁴	X ⁴	X ⁴	X ⁴	X ⁴	X ⁴	X		
Vital Signs ²	X	X	X	X	X	X	X	X	X	X	X	X		
Pregnancy test ³	X	X ⁴			X ⁴	X ⁴	X ⁴	X ⁴	X ⁴	X ⁴	X ⁴	X		
Hematology ³	X	X ⁴			X ⁴	X ⁴	X ⁴	X ⁴	X ⁴	X ⁴	X ⁴	X		
Chemistry ³	X	X ⁴			X ⁴	X ⁴	X ⁴	X ⁴	X ⁴	X ⁴	X ⁴	X		
Coagulation Parameters ³	X	X ⁴			X ⁴	X ⁴	X ⁴	X ⁴	X ⁴	X ⁴	X ⁴	X		
Thyroid Function ³	X	X ⁴			X ⁴	X ⁴	X ⁴	X ⁴	X ⁴	X ⁴	X ⁴	X		
Urinalysis ³	X	X ⁴			X ⁴	X ⁴	X ⁴	X ⁴	X ⁴	X ⁴	X ⁴	X		
Cytokines ⁵		X			X	X	X	X	X	X	X			
JTX-2011 ⁶		X			X	X	X	X	X	X	X			
Pembrolizumab ⁷		X			X	X	X	X	X	X	X			
IP ⁵	X	X		X	X	X	X	X	X	X	X			
TE ⁵	X	X		X	X	X	X	X	X	X	X			
PK ⁵		X		X	X	X	X	X	X	X	X			
ADA ⁵		X			X	X	X	X	X	X	X			
Archival Tumor Tissue ⁵	X													
Fresh Biopsy ⁵	X													
NAB ⁵		X			X	X	X	X	X	X	X			

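### Protocol 7.2.9 lists ipilimumab in Parts E and F at Cycle 3 Day 1 and every later Day 1 with no condition, although the four permitted doses are already used by Cycle 2 Day 22

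*Protocol*

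**What the plan says.** Every place in the protocol that states a total for ipilimumab gives four:

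- Section 3.4 sets the regimen as "3 mg/kg q3w for a total of four doses".
- The synopsis, for Part E, says "ipilimumab will be administered IV q3w for a maximum of 4 doses".
- Section 5.3, also for Part E, says "ipilimumab will be administered IV q3w for up to 4 doses". Section 5.7 gives the same limit for Part F.
- Table 13 footnote 17 covers doses missed at C1D22, C2D1 or C2D22: "they can be made up q3w beginning on C3D1. Each subject may receive up to four total doses of ipilimumab". Table 16 carries the same footnote for Part F.

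The visit procedures list ipilimumab for Parts E and F at C1D1 (7.2.1: "Ipilimumab administration followed by observation for at least 1 hour"), C1D22 (7.2.6), C2D1 (7.2.7) and C2D22 (7.2.8). Section 7.2.9, which covers C3D1 and Day 1 of all later cycles, lists it again for Parts E and F: "Ipilimumab Administration followed by observation for at least 1 hour". Section 7.2.10, which covers Day 22 from Cycle 3 on, has an entry headed "Parts C, E, and F only" that contains vital signs and no ipilimumab.

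**The concern.** A visit list is what a site works from on the day. As written, 7.2.9 instructs a dose that the dosing section does not allow for a subject who has missed none. The drug is one that section 1.6.3 describes as able to cause severe and even fatal immune-mediated toxicity. If the line is meant for make-up doses, the two visit lists still do not deliver the 3-week make-up interval in the footnotes, because no ipilimumab is listed on the intervening Day 22.

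There is also a consequence for analysis. Relative dose intensity in SAP 9.8.3 divides by a planned dose per cycle. For ipilimumab from Cycle 3 on, in a subject with no missed dose, that planned dose is zero under the four-dose limit and 3 mg/kg per cycle under 7.2.9. The SAP does not say which applies.

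**Working it through.** **Inputs.** JTX-2011 cycle in Parts E and F: 6 weeks, or 42 days (5.3, 5.7). Ipilimumab: 3 mg/kg per dose, maximum four doses, every 3 weeks (3.4). Dosing visits: 7.2.1 and 7.2.6 to 7.2.10. Study day of Cycle c Day d = 42 × (c − 1) + d.

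**Step 1: reproduce the plan's own figure.** C1D1, C1D22, C2D1 and C2D22 fall on study days 1, 22, 43 and 64. That is four doses at intervals of 21 days, totalling 4 × 3 = 12 mg/kg. It matches the stated regimen exactly, and nothing remains after C2D22 if no dose is missed.

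**Step 2: add 7.2.9 as written.** Doses through Day 1 of Cycle k = 4 + (k − 2), for k of 3 or more.

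| Through | Study day | Doses | mg/kg |
|---|---|---|---|
| C2D22 | 64 | 4 | 12 |
| C3D1 | 85 | 5 | 15 |
| C4D1 | 127 | 6 | 18 |
| C5D1 | 169 | 7 | 21 |

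The limit is passed at C3D1, and the total then rises by one dose per cycle for as long as treatment continues. Section 5.3 continues JTX-2011 in Part E until discontinuation criteria are met, so Cycle 3 and beyond are foreseen.

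**Step 3: try the make-up reading.** Under the footnotes, make-up doses are 21 days apart from C3D1. Under 7.2.9 and 7.2.10 the only visits listing ipilimumab are Day 1 visits, 42 days apart.

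| Doses missed | Footnotes | 7.2.9 and 7.2.10 |
|---|---|---|
| 1 | C3D1 (day 85) | C3D1 (day 85) |
| 2 | C3D1, C3D22 (days 85, 106) | C3D1, C4D1 (days 85, 127) |
| 3 | C3D1, C3D22, C4D1 (days 85, 106, 127) | C3D1, C4D1, C5D1 (days 85, 127, 169) |

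The two agree for one missed dose and differ for two or three. Section 7.2.10 is not written for an ipilimumab infusion in other respects either: it asks for weight and for vital signs before and after infusion in Part H only, whereas 7.2.8 asks for both in Parts E and F.

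**Step 4: compare the surrounding text.** Section 7.2.9 does qualify other lines: RNA sampling is tied to named cycles and PSA to prostate cancer subjects. The ipilimumab line has no such qualifier. The vital-sign footnotes also differ. Footnote 3 of Table 13 names C1D22 and C2D22 as the days on which ipilimumab is given alone. Footnote 2 of Table 16 refers to Day 22 of each cycle for pembrolizumab or ipilimumab alone. The ipilimumab rows of Tables 13 and 16 are broken in the text available, so nothing here rests on which columns are marked.

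**Step 5: timing against Part E decisions.** DLTs are counted in the first cycle (6.3), and evaluability needs completion through C2D1 (6.2), which is day 43. The earliest possible fifth dose is day 85.

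**The case against.** The strongest reply is that the limit is not in doubt. It appears in the synopsis, the dosing section, both study-design sections and both schedule footnotes, and no section states a total above four. The line in 7.2.9 has an evident purpose, because make-up doses may start at C3D1 and so ipilimumab has to be available there. Table 13 footnote 18, the matching Table 16 footnote and footnote 1 of Tables 21 and 22 ask for ipilimumab samples from C3D1 only if the drug is given, so they treat such dosing as conditional. On this view, 7.2.9 lacks only a cross-reference. The make-up footnote is also permissive, and SAP 9.8 summarises exposure, so any excess would show.

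Most of this stands as mitigation. It makes the make-up purpose the likely one, and many sites would probably have stopped at four. It does not remove the conflict: 7.2.9 states no condition, and the make-up reading still leaves 7.2.10 out of step with the footnotes for two or more missed doses.

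A reader might infer more: that subjects were in fact overdosed, or received twice the maximum. The documents do not support that. They contain no exposure data. Doubling (8 doses, 24 mg/kg) needs treatment to C6D1 and a breach of the limit at four successive visits, and Cycle 6 is an arbitrary stopping point.

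**Conclusion.** The inconsistency is real and should be corrected, with a limited reach. On a literal reading, a subject with no missed dose exceeds the protocol's own limit by one dose (3 mg/kg on top of 12 mg/kg) at C3D1, and by one further dose per 6-week cycle. A subject with two or three missed doses has make-up intervals of 3 or 6 weeks, depending on the section followed.

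This rests on reading 7.2.9 and 7.2.10 as they stand and on a 42-day cycle. The documents do not show how sites applied them.

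Two wider conclusions a reader might draw do not follow. First, Part F results are not at risk, because SAP section 4 says Part F never opened. The affected group is at most the Part E subjects who reached Cycle 3, out of about 18 planned (5.3); the number who did is not given. Second, the Part E Cycle 1 DLT counts and the escalation decisions based on them are not compromised, because any extra dose falls at day 85 or later. SAP section 4 also says that the Phase 1 parts were completed according to the design, but that general statement does not settle how many ipilimumab doses each subject received.

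**What to change.** Reconcile 7.2.9 and 7.2.10 with 3.4, 5.3, 5.7 and the make-up footnotes to Tables 13 and 16, so that the visit lists, the total number of ipilimumab doses and the timing of make-up doses agree. The two vital-sign footnotes should be aligned at the same time. This review does not say which dosing rule is right; that is for the sponsor's clinical team.

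Because Part E is complete, wording alone no longer reaches its subjects. Check the Part E dosing records, and report any subject with more than four ipilimumab doses and any differing make-up intervals. State in the SAP what planned ipilimumab dose enters the relative dose intensity from Cycle 3 on.

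The cost is small: a few lines in two visit lists, one sentence in the SAP, and one listing from dosing data that SAP 9.8 already uses.
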